### **13.4.2 General Convention**

#### **13.4.2.1 General Rules for Handling of Missing, Unused or Inconsistent Data**

In general, missing values will remain as missing, i.e., no attempt will be made to impute missing values and only observed values will be used in data analyses and presentations. Specific rules for handling missing efficacy data are described in Section 13.7.1.2.1.

#### **13.4.2.2 Other Specific Conventions**

### **13.5 Demographic and Baseline Characteristics**

No specifics other than the trial inclusion parameters.

#### **13.5.1 Patient Demographic Characteristics, Medical History and Diagnoses**

Baseline characteristics will be described using the ITT population. Demographics, medical history and other baseline variables will be summarized as appropriate to the type of data.

#### **13.5.2 Previous Medications**

In order to further characterize the study population, the incidence of the use of selected medications should be disclosed by the participant to include: Any current or passed drugs directly prescribed or used to treat cystic fibrosis (CF).

### **13.6 Investigational Product and Concomitant Therapy**

Not applicable to this Clinical Trial.

### **13.6.1 Investigational Product**

#### **13.6.1.1 Extent of Exposure**

The duration of study medical device treatment (accounting for permanent discontinuation) will be summarized. The number of participants on treatment over time will be summarized. The total patient years on study medical device will also be calculated

#### **13.6.1.2 Measurement of Treatment Compliance**

Treatment compliance for each patient will be calculated as the number of days study medical device was actually used (ie, number of days on treatment minus days of temporary discontinuation) divided by the number of days of follow-up, allowing for early permanent discontinuation of study medical device when applicable. Study medical device discontinuation is defined as a minimum of 3 consecutive days without study medical device intake. The percentage of participants at least 80% compliant will also be reported.

### **13.6.2 Concomitant Medication/Therapy**

Not recommended for this Clinical Trial - however, if deemed medical necessary then the appropriate treatment should be administered as ordered by the physician.

## **13.7 Efficacy/Activity Analysis**

The main efficacy measurement shall be a reduction the appearance of cystic fibrosis (CF).

### **13.7.1 Primary Efficacy Variable(s)**

A reduction in the appearance of cystic fibrosis (CF).

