### **5. STUDY OBJECTIVES**

#### **5.1 Primary Objective**

To specifically illustrate and measure both clinical and empirical efficacy described by (AARC) in the Clinical Practices Guidelines for Postural Drainage Therapy (1991) for external manipulation of the thorax for postural drainage therapy and the secretion clearance, or presence of atelectasis caused by mucus plugging.

Outcome measured by:

Percentage change of oxygen levels in the blood (pulse oximetry). SpO2 will be monitored using the standard pulse oximeter system (K131111). Change from baseline before treatment and measure again up to 3.5 hours after treatment.

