### **7.2 Inclusion Criteria**

- Previously diagnosed with cystic fibrosis (mild, moderate or severe)
- Prescribed (licensed medical provider) airway clearance device/system for at home, self-treatment for airway clearance
- Physically able to perform self-treatment or treatment by an at home medical provider

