### **9.1.1 Efficacy Criteria**

Primary: Physical exam by medical practitioner for initial diagnosis and changes in spirometer reading from before treatment compared to reading three (3) hours after treatment. In addition, changes in iHealth Air pulse oximeter (FDA 510k K131111) reading from before treatment compared to reading three (3) hours after treatment.

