### **9.1.2 Clinical Assessment Methods**

Primary: Measurements of before and after with pulse oximetry device and spirometer.

Secondary: Participant surveys completed.

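### Sections 13.7 and 13.7.1 name a primary efficacy variable, reduced appearance of cystic fibrosis, that is undefined, tied to no planned assessment, and in conflict with the primary objective and with the endpoint the plan analyses

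*Protocol*

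**What the plan says.** Section 13.7 of the protocol opens its efficacy analysis with "The main efficacy measurement shall be a reduction the appearance of cystic fibrosis (CF". Section 13.7.1, under the heading for the primary efficacy variable, repeats it: "A reduction in the appearance of cystic fibrosis (CF". Nothing further is said about what appearance means.

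Elsewhere the protocol describes primary efficacy differently. The outcome under the primary objective (5.1) is "Percentage change of oxygen levels in the blood (pulse oximetry", read before treatment and again up to 3.5 hours afterwards. Section 9.1.1 lists "Physical exam by medical practitioner for initial diagnosis and changes in spirometer reading from before treatment compared to reading three (3) hours after treatment" and adds the pulse oximeter change over the same three hours. Section 9.1.2 gives the methods as "Primary: Measurements of before and after with pulse oximetry device and spirometer" and "Secondary: Participant surveys completed". Section 9.1.1.1 names a composite rate of success together with absence of safety problems. Section 9.1.2.1, where the components of the primary endpoint should be defined, is marked not applicable.

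Section 13.7.1.1, directly beneath the appearance wording, describes the primary endpoint as the first adjudicated skin problem, allergic reaction or new medical condition. Every participant enters with the disease: "Previously diagnosed with cystic fibrosis (mild, moderate or severe" (7.2). The SAP names no endpoint. It sets summary conventions and a two-sided 5% level.

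**The concern.** A primary variable has to be something the trial records, on a stated scale, at a stated time. The one named in 13.7 and 13.7.1 is not. It also sits directly above a different endpoint, and the methods that follow are written for that other endpoint.

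The primary claim of efficacy is at stake. Section 13.7.1.2.4 allows formal tests of the secondary endpoints only if primary efficacy is significant, so confusion over the primary variable passes down to FVC and FEV1. Section 2.0 says the trial is meant to support a request for a new reimbursement code, so a reader of the results will look for an efficacy finding that was fixed in advance. With several candidate primary outcomes in the protocol, a later choice among them would not be prespecified.

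**Working it through.** The plan gives no figure for the appearance variable. Its only related number is the sample size of 70. Section 13.2 supports it by reference to a population of 30,000 and to earlier trials, and states no power, effect size, standard deviation or event rate. It cannot be reproduced from any version of the primary variable. Read as precision for a proportion of 0.5 at 95% confidence with a finite-population correction, n = n0/(1 + (n0 − 1)/30,000), where n0 = 1.96² × 0.25/m². A margin m of 0.10 gives 96 and a margin of 0.05 gives 380; neither is 70. The point therefore rests on setting the sections side by side.

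**Step 1: is the variable defined?** Sections 13.7 and 13.7.1 give no unit, scale, assessor, visit or responder rule. Section 9.1.2.1 is not applicable. The SAP adds nothing.

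**Step 2: is any assessment linked to it?** Section 9.1.2 lists oximetry, spirometry and surveys, and no section connects any of them to appearance. The physical examination in 9.1.1 is "Physical exam by medical practitioner for initial diagnosis", and 12.1.2 records examination abnormalities at baseline. Follow-up in 12.3 is a call, an email, a written summary and a later courtesy email. No repeat examination is described.

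**Step 3: what could it mean?**
- Presence of the disease: fixed by the entry criterion in 7.2. It would not change over the 21 days of participation in 6.2.
- Signs or severity: 7.2 grades the disease in three classes, so change is possible in principle. No later grading is planned, so there would be nothing to compare with baseline.

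**Step 4: how does it fit the other statements?** The protocol contains five accounts of primary efficacy:
1. SpO2 change (5.1).
2. Spirometer and oximeter change, with an examination (9.1.1).
3. Composite success rate plus safety (9.1.1.1).
4. Reduced appearance of the disease (13.7, 13.7.1).
5. First occurrence of an adverse event from a list of three (13.7.1.1).

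**Step 5: which one is analysed?** Censoring at the last assessment (13.7.1.2.1), Kaplan-Meier curves with a log-rank test at 0.05 (13.7.1.2.3) and Cox models (13.7.1.2.5) are time-to-event methods. They fit only the fifth account. Section 8.3 assigns everyone to one arm, so the log-rank test has no second group to compare, and the treatment term in the Cox model does not vary. No step in 13.7 analyses a before-after change in SpO2. Section 13.7.2.2 applies the same time-to-event methods to the secondary endpoints.

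**Step 6: what would a measurable primary variable allow?** For a paired mean change at two-sided 0.05 with n = 70, the detectable standardised change is (1.96 + z_power)/√70. With power assumed at 80% this is (1.960 + 0.842)/8.367 = 0.33 SD; at 90% it is (1.960 + 1.282)/8.367 = 0.39 SD. The documents state neither the power nor the SD of the SpO2 change, so this is context only. It assumes all 70 supply a pair of readings.

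**The case against.** The best defence is that 13.7.1.1 supplies an operational endpoint. Its events are recorded and adjudicated, the steps beneath it are written for it, and no analysis step uses the word appearance. On that view the wording in 13.7 and 13.7.1 is a harmless leftover. Part of this stands. A reader might infer that the analyst would have to report no reduction or invent a measure, and the documents do not support that: the analyst could follow 13.7.1.1 and summarise the adverse-event composite. But that composite counts harms, and it is neither the variable in the heading above it nor the outcome of 5.1. The conflict remains.

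A reader might also infer that the variable is constant and the trial has no power, because the diagnosis is fixed at entry. That substitutes diagnosis for appearance. The text does not say diagnosis, and the severity classes in 7.2 leave room for a reading that could vary. Nor can it be said that the planned instruments have no bearing on the disease. Section 4.12 describes such conditions by excess mucus and declining lung function, and spirometry and oximetry relate to those manifestations. What the documents support is narrower: the variable is undefined, and no instrument is assigned to it.

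SpO2 is also not the only candidate for a replacement. Section 9.1 states the goal in terms of the spirometer, and 9.1.1 and 9.1.2 list both devices as primary. That is fair. SpO2 is proposed because it is the outcome attached to the primary objective, with spirometry attached to the secondary one (5.2); the sponsor has to confirm it.

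Finally, 13.1 allows the plan to be revised on blinded review before data lock. In a single arm with open before and after readings, anyone who sees the pooled data sees the effect, so a choice made at that stage is weak protection.

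**Conclusion.** The concern holds as a fault of definition and consistency, and the text is wrong as written rather than merely short of detail. Sections 13.7 and 13.7.1 name a primary efficacy variable that has no definition and no planned assessment linked to it. It conflicts with four other accounts of primary efficacy in the same protocol. The analysis in 13.7.1.2 is aimed at the adverse-event composite, so the plan yields no primary efficacy result on the outcome of its own primary objective.

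Its size is not a power or sample-size figure, because the documents give none for this variable. It is one primary claim with five competing definitions, of which the one analysed is a safety measure. The conclusion rests on the text alone. It assumes only that no separate manual, outside the two documents, defines the appearance variable or schedules a re-grading.

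**What to change.** 1. Delete the appearance wording in 13.7 and 13.7.1. Name the outcome of 5.1 instead: percentage change in SpO2 from the reading before treatment to the reading after it. Say whether this is a relative change or a difference in percentage points.
2. Fix one reading time, reconciling up to 3.5 hours in 5.1 with three hours in 9.1.1.
3. State which treatment session is used, or that a within-participant average over sessions is used. Section 8.11 pays for each day on which data are sent, so repeated readings are expected. Section 13.4.1.3 defines baseline as the last value before first use, which would not be the pre-session reading at later sessions.
4. Make 9.1.1, 9.1.1.1, 9.1.2.1 and 13.7.1.1 agree with this variable. Keep cystic fibrosis status as an entry criterion only.
5. Report skin, allergic and new-condition events as safety outcomes under 13.8.
6. In 13.7.1.2.3, replace the log-rank test with a paired within-participant analysis and a 95% confidence interval. Replace the censoring rule in 13.7.1.2.1 with a rule for participants who lack a pair of readings, and revise the Cox subgroup models in 13.7.1.2.5 to match.
7. Keep FVC and FEV1 secondary as in 5.2, with 13.7.2.1 and 13.7.2.2 rewritten for before-after change. Restate the basis for 70 in 13.2 in terms of the new primary variable, and carry the definition into the SAP.

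The cost is edits to several linked protocol sections and the SAP. Oximetry and spirometry are already planned, so no new data, visits or patients are needed. The changes should be made before anyone reviews the before and after readings.

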#### **13.7.1.1 Description of the Primary Variable(s)**

The primary efficacy endpoint is the composite cluster of the first occurrence, over the duration of study (randomization to study end date inclusive), of the following adjudicated events:

- Any skin conditions caused by the device to include irritations,
- Any allergic reactions,
- Any new medical conditions during the study.

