#### **4.3 Rationale for this Trial Design**

Since this study is designed to illustrate the efficacy of the device for the current 510K indications in a single arm, large sample multisite study. A placebo control is not required since each subject will serve as a before and after treatment with measurable indicators.

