# **6. STUDY DESIGN**

## **6.1 Description of the Protocol**

The present study is designed as a multi-center, non-randomized, single-blind, one arm group trial with 70 participants per arm.

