### **8.3 Method of Assigning Participants to Treatment Group**

N/A - All included shall be assigned to the single arm.

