### **13.7.1.2 Primary Analysis**

#### **13.7.1.2.1 Handling of Dropouts or Missing Data**

All randomized participants will be included in the primary ITT efficacy analysis. Participants not reaching the primary efficacy endpoint by the study end date, or before their last assessment for participants lost to follow-up, will be censored at the date of their last assessment visit.

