#### **13.7.1.2.3 Main Statistical Model and Adjustment for Covariates**

For the primary analysis, all adjudicated events occurring from randomization to the study end date (inclusive) will be counted, including events occurring after early permanent discontinuation of study medical device. The proportion of participants remaining event-free over time will be displayed in the form of survival curves using the Kaplan-Meier method and analyzed (primary analysis) using a two-sided log-rank test. Statistical significance will be claimed if the computed p-value is equal to or less than 0.05.

The number and percentage (crude rate) of participants experiencing a primary endpoint will be summarized.

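### The primary efficacy endpoint in section 13 is a set of harms, not the SpO2 change of section 5.1, and its log-rank test cannot be computed in a single arm, so the plan formally tests no efficacy endpoint

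*Protocol*

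**What the plan says.** Section 5.1 of the protocol measures the primary objective by "Percentage change of oxygen levels in the blood (pulse oximetry"), read before treatment and up to 3.5 hours after. Section 4.3 justifies having no control group on the ground that "each subject will serve as a before and after treatment with measurable indicators". The design is a "one arm group trial with 70 participants per arm" (section 6.1), and section 8.3 confirms: "All included shall be assigned to the single arm".

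The statistical section describes a different trial. Section 13.7.1.1 reads: "The primary efficacy endpoint is the composite cluster of the first occurrence, over the duration of study (randomization to study end date inclusive"). The listed events begin with "Any skin conditions caused by the device to include irritations" and continue with allergic reactions and new medical conditions. Participants without an event "will be censored at the date of their last assessment visit" (section 13.7.1.2.1). Event-free proportions are shown by Kaplan-Meier and "analyzed (primary analysis) using a two-sided log-rank test" (section 13.7.1.2.3). Section 13.7.1.2.4 tests two secondary endpoints only if the primary is significant. Section 13.7.1.2.5 adds Cox models with treatment and treatment-by-covariate terms. Section 13.7.2.2 gives the secondaries the same method as the primary.

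Further versions of the primary appear elsewhere:
- physical exam, spirometry and oximetry (9.1.1);
- an undefined success composite with a safety remark (9.1.1.1);
- oximetry and spirometry (9.1.2);
- a lessened appearance of cystic fibrosis (13.7 and 13.7.1).

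Section 9.1 makes spirometry the goal of the trial. Section 9.1.2.1, which should define the components of the primary endpoint, is marked not applicable. The SAP sets two-sided 5% testing and lists summary statistics, including a 95% CI for continuous variables. It names no endpoint and no test.

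**The concern.** Two faults combine. First, the endpoint that section 13 calls primary efficacy consists of harms. A low rate of skin irritation or allergy is a safety result; it does not show that the device clears airways or raises SpO2. Second, the test chosen for it compares survival curves between groups, and the trial has only one group.

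Because the secondaries are tested only after a significant primary, a primary test with no value blocks all the others. With several primaries on paper, which result counts as the trial's answer would be open to choice after the data are seen.

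There is a safety consequence too. Sections 10.1 and 13.8.1.2 record all adverse events and summarise them. Section 10.3 and the Safety Review text of Appendix 5 treat efficacy endpoints or outcome events as separate from adverse events. With harms named as the efficacy endpoint, it is unclear whether they would be reported as adverse events at all.

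**Working it through.** **Inputs.** One arm, N = 70 (6.1, 8.3); two-sided 5% level (13.7.1.2.3, SAP); no imputation (13.4.2.1); no replacement of participants who stop the device (11.2). The documents give no SD, effect size, event rate, hazard ratio, reference curve, power or missing-data rate.

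**1. The plan's own figure.** Section 13.2 asserts 70 from a target population of 30,000 and prior trials. With no effect size, variability or power, it can be neither reproduced nor refuted. As an illustration, the Schoenfeld formula for a hypothetical two-arm 1:1 trial with 80% power needs 4(1.960 + 0.842)²/(ln HR)² events. That is 66 at an assumed hazard ratio of 0.50 and 70 at 0.51. Those are events rather than participants, they need a second arm, and neither hazard ratio is in the documents.

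**2. Log-rank test in one arm.** At each event time let n be the number at risk, n1 the number at risk in the index group, and d the number of events.
- Expected events: E = d × n1/n.
- Variance: V = d × (n1/n) × (1 − n1/n) × (n − d)/(n − 1).

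With everyone in one group n1 = n, so E = d and V contains the factor 1 × 0 = 0. Summed over event times, O − E = 0 and V = 0. The statistic is 0/0 and there is no p-value. A simulated data set of 70 participants with 12 events gave O − E = 0 and V = 0.

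**3. Cox subgroup models (13.7.1.2.5).** In one arm treatment = 1 for all, so the linear predictor is b1 + b2·x + b3·x. The constant b1 cancels from the partial likelihood, and only the sum b2 + b3 is identified. For a covariate with one degree of freedom the information matrix has rank 1 for 3 terms. The treatment and interaction terms cannot be estimated.

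**4. Consequence for the secondaries.** The condition in 13.7.1.2.4 can never be met. Even if it were, 13.7.2.2 applies the same event method, and the event list in 13.7.2.1 ends at its colon with nothing after it. No test of change in SpO2, FVC or FEV1 appears anywhere in section 13.

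**5. What the before/after design could deliver.** For a one-sample t-test on one change value per participant, the 95% CI half-width is t(0.975, n − 1)/√n in units of the SD of the change. For n = 70 that is 1.995/8.367 = 0.238. Detectable mean changes come from the noncentral t distribution. The rows for 63 and 56 assume that 10% and 20% have no usable reading.

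| Evaluable n | CI half-width (SD) | 80% power (SD) | 90% power (SD) |
|---|---|---|---|
| 70 | 0.238 | 0.340 | 0.393 |
| 63 (70 × 0.9) | 0.252 | 0.359 | 0.415 |
| 56 (70 × 0.8) | 0.268 | 0.381 | 0.441 |

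If the SD of the SpO2 change were 1, 2 or 3 points (assumed), the change detectable with 80% power at n = 70 would be 0.34, 0.68 or 1.02 points.

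**The case against.** The strongest reply is that the SAP already gives enough: a 95% CI on mean change excludes zero exactly when a one-sample t-test is significant at 5%. That equivalence is true, and the data could support a test. But the SAP sentence is a generic table format. It ties the CI to no variable, time point or rule for repeated readings, and it does not replace the primary test or the gate in section 13.

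A second reply is that section 13.1 allows revision after blinded review and promises a final plan before data lock. This helps only partly. Section 13 is stated to be the basis of that plan, the SAP provided does not resolve the conflict, and blinded review protects little when everyone is known to receive the device.

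Third, a one-sample log-rank test exists. It needs a pre-specified reference survival curve, and none is given.

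Fourth, six versions of the primary may be too many. Section 9.1.2 names the same instruments as 9.1.1, and 9.1.1.1 could be read as the event-free side of the composite. On that reading about four remain, which is still too many.

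Some side points are imprecision rather than contradiction. Three hours (9.1.1) lies within up to 3.5 hours (5.1). The single baseline of 13.4.1.3 can fit 5.1 if there is only one pre-treatment reading. The waiver in 10.3 may be meant as an exception to 10.1. These need clarifying, but the main finding does not depend on them.

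**Conclusion.** The concern holds and must be fixed before analysis. The conflict between 5.1 and 13.7.1.1 is plain on the page, and the failure of the log-rank test is algebraic; it does not depend on any assumed event rate. Followed as written, the plan yields descriptive summaries of SpO2 and lung function but no formal test of any efficacy endpoint.

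The statement concerns the plan, not the data: paired readings would allow a test if one were pre-specified. The figures of 0.24 SD (half-width) and 0.34 SD (80% power) describe that replacement analysis with all 70 evaluable. At 10% to 20% missing (assumed) they become 0.25 to 0.27 SD and 0.36 to 0.38 SD. Whether that is adequate cannot be judged until the sponsor states an SD and a change worth detecting.

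**What to change.** 1. **Name one primary** and use it in 5.1, 9.1, 9.1.1, 9.1.1.1, 9.1.2, 9.1.2.1, 13.7, 13.7.1, 13.7.1.1 and the SAP. Within-participant SpO2 change is the natural choice because it is the stated primary objective; the sponsor should confirm it against the spirometry wording in section 9. State a single measurement time, and reconcile the one baseline of 13.4.1.3 with before/after readings. Say how repeated readings form one value per participant (for example the mean change) or enter a mixed model with a participant effect. The days of data used must be reconciled across 6.2 (21 days), 12.3 (one month) and the payment cap in 8.11 (210/7 = 30 paid days).
2. **Replace the censoring, log-rank and Cox text** in 13.7.1.2.1, 13.7.1.2.3, 13.7.1.2.5 and 13.7.2.2 with a paired or one-sample test of mean change, a 95% CI and a rule for missing readings. Report subgroups as mean change with CI. Complete 13.7.2.1 with an ordered list of secondaries. FVC and FEV1 would fit the count of two in 13.7.1.2.4; the sponsor should confirm this and say whether the survey in 9.1.1.2 is descriptive or joins the order.
3. **Move the harm composite to 13.8** as a descriptive safety summary, delete the wording on the appearance of cystic fibrosis, and reconcile 10.1, 10.3, 13.8.1.2 and Appendix 5 on whether these events are adverse events.
4. **Restate the basis for N** in 7.1 and 13.2 as precision and power for a mean change, with the assumed SD.
5. **Revise the Clinical Events Committee's role** in 6.4 and Appendices 4 and 5, for example to safety events and cause of death.

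The cost is wording in the protocol, SAP and committee documents. The oximetry, spirometry and surveys are already named as outcomes, so no new type of measurement is needed, but section 12.3 does not schedule the readings and should. Nothing here by itself requires a change from 70. The sponsor must commit to one primary and supply an SD.
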